Device, of small size, approximately 20 cm wide, 14 cm deep and 20 cm high, equipped with a broad spectrum of Ultraviolet-Visible (190-840 nm) for micro volumes of 0.5 to 2 microliters of sample initial through fiber optics. It has the measurement of very concentrated samples without the need of previous dilutions. The quantification of the absorbance of oxyhemoglobin at 414 nm will be measured by dropping one to two microliters of the substance to be analyzed. On this substance the device emits a beam of light that crosses the sample. Depending on the beam of light traversed and, therefore, received, it is considered transmittance. Although the transmittance leads to losses due to dispersion in the solution, it is considered, according to the Lambert-Beer Law, that the transmittance and absorbances are inversely related. Absorbance is the intensity of light that the chemical component of the sample retains and, therefore, is the opposite of the received light. As a consequence, the absorbance is measured with the opposite of the logarithm of the transmittance, expressed as follows: $A = -\log T$

It will be necessary to use the centrifuge Hermle z326K, centrifuge with possibility of cooling. Automatic pipettes of different microliter ranges from the Eppendorf Research Plus brand.

Tubes whose additive is dipotassium ethylenediaminetetraacetic acid (K2-EDTA) that will be centrifuged at 3500 revolutions per minute (rpm) for 10 minutes at 4 ° C will be used.

The plasma of the blood samples will be transferred to aliquots with a capacity of approximately 1.4 ml. The biological material to be transferred will be approximately 1 ml, regardless of the one obtained. The remaining plasma will be discarded to a biological container and destroyed according to the usual procedure and marked by the clinical trial with drugs.

The pertinence of this material resource could be justified by the following:

1. Coverage in the Clinical Trials Unit and Collaborating Researchers.

- 2. Acceptable capital, compared to other methods.
- 3. Objective method and sensitive to changes supported by Janish S et al (52).

2. Photoshop CC.

Application intended for the identification of the color of photographs. The program outputs the values in RGB and CMYK automatically.

3. Photographic camera

The photographs will be taken through the SONY® SLT-α58 camera with HD CMOS sensor and RGB filter with CE marking.

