14.2.2. Statistical power and calculation of sample size

The choice of this secondary variable could be justified as the main one due to its statistical power, in relation to the sample size calculation, in order to conclude with a statistical

significance. That is, the sample size calculated for this variable could be included in the sample size calculated for the main variable; using the same fieldwork

According to a study (52) at a cutoff point for evaluation of free hemoglobin in plasma through absorbances and visual detection, the following is stated: of fifteen samples detected with absorbances, eight of them were not detected visually. That is, the visual inspection shows a predictive positive values (PPV) of 46.6%. It is tried to prove the veracity of this assumption and for it the following verification of hypothesis, of bilateral type is proposed:

H0: The positive prediction of intensity of hemolysis through visual stages is not optimal.

H1: The positive prediction of intensity of hemolysis through visual stages is optimal.

A calculation of GRANMO samples (63) has been carried out in the modality of proportions observed with respect to a reference. With an alpha error of 5% and a power of 1%, bilateral test. The reference proportion is 0.466 (52) and the objective is to reach a positive prediction of at least 0.80; It is considered optimal to detect the intensity of hemolysis in each stage. Therefore, the minimum difference to be detected is obtained through the objective of 0.80 - 0.466, that is, 0.334. Finally, it is obtained that at least 41 individuals are needed or, what is the same, 49 blood samples with a predicted proportion of losses of 20%; corresponds to possible samples with insufficient blood content for inspection.

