The use of spectrophotometry is considered pertinent, although it is not the most discriminative technique currently used for the quantification of absorbances, if it is identified as discriminative and widely used for its price-quality ratio. In spite of having a sensitivity of 48% according to Shash JS et al., The rest of the precision values of this diagnostic technique are within the ranges considered acceptable (52). Their positive / negative likelihood ratios are unknown in order to extrapolate these results and, therefore, those that they expose would be distorted by the sample used in their research.

Shah JS et al. and other authors, in the last years of research in this field, affirm the relevance of the absorbance technique for the detection of hemolysis as greater precision than the concentrations, as it was done (51,52,53).

In addition, in the institution where the fieldwork is planned, it has access to said device and procedure, available and economically feasible, through a collaborating researcher of the present study.

The first samples obtained from the first volunteers included in this study will not be possible to subject them to visual inspection of the observers; it would still be in the design phase. However, these will be analyzed with spectrophotometry and photographed, so they would be measured equally but objectively.

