14.2.3.3.2. Validity analysis

A. VALIDITY OF APPEARANCE.

To address the convenience of stages, it has been based on literature; They are considered experts in the subject. It will be reflected in section 14.2.3.

B. VALIDITY OF CONTENT.

We intend to evaluate if the items represent those that we want to measure, that is, increase in intensity of hemolysis. A correlation between visual stages and intensity scores could be used. assessed in 14.2.1.2. B.

B. VALIDITY OF CRITERIA.

We intend to evaluate the concordance between the measures by absorbances and those made by the observers. It is intended to calculate sensitivity, specificity, positives and negatives values of the visual inspection.

C. CONSTRUCT VALIDITY.

A possible convergence or divergence of versions one and two will be assessed. In the case of finding a convergence between two of scales, the one that higher value of concordances will be the one that will be used for the verification of hypothesis.

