14.2.3.4. Methodology of the design and validation of the scale of hemolysis

It is considered that the methodology used to carry out the validation of the scale could be justified by the guide of studies of diagnostic precision STARD (66). This guide addresses studies in which what is intended to be studied is evaluated with a clinical or gold standard reference (64). The steps specified in the guide are followed to ensure that the results and conclusions are valid, as well as the consideration of their applicability.

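### The haemolysis validation can show agreement of the visual scale with absorbance, not accuracy for haemolysis, and the proportion it tests is mislabelled as a predictive value

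*Combined protocol and SAP*

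**What the plan says.** All places are in the combined protocol and SAP.

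- Section 9.7.3 lists reasons for using the spectrophotometer. One is "Objective method and sensitive to changes supported by" reference 52.
- Section 14.2.3.2 returns to the technique: "In spite of having a sensitivity of 48% according to" a study, also numbered 52, its remaining accuracy values are called acceptable. It adds that likelihood ratios are unknown, so the results cannot readily be extrapolated, and that the published values would be distorted by that study's sample. It does not give the cut-off or the standard behind the 48%.
- Section 14.2.3.3.2, under criterion validity: "We intend to evaluate the concordance between the measures by absorbances and those made by the observers". It continues: "It is intended to calculate sensitivity, specificity, positives and negatives values of the visual inspection".
- Section 14.2.1 defines the stages by ranges of absorbance and states that plasma free-haemoglobin concentration will be neither measured nor analysed.
- Section 14.2.2 takes a reference proportion of 0.466 and says "the objective is to reach a positive prediction of at least 0.80". Its H1 is that visual stages give an optimal positive prediction of haemolysis intensity. The 0.466 comes from 15 samples positive by absorbance, 8 of which were missed by eye, and is labelled a positive predictive value.
- Section 14.2.3.4 relies on a diagnostic-accuracy guideline for studies "evaluated with a clinical or gold standard reference".

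**The concern.** Visual haemolysis intensity is the main secondary variable and has its own hypothesis and sample size. Section 4.2 justifies the new scale as a precise and valid way to detect haemolysis intensity, and section 14.3 then uses intensity as an outcome for comparing the venipuncture methods.

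The plan reports a low sensitivity for its only criterion and then uses that criterion as if it were error-free. Two kinds of mistake could follow. A visual call that is right about haemolysis can be scored as wrong because absorbance missed the sample. A scale that merely reproduces absorbance, including its misses, would look faultless. With no second standard in the trial, the data cannot separate these cases. A reported sensitivity, specificity or predictive value would invite a claim about haemolysis that the design cannot carry.

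The tested quantity is also not pinned down. The label in 14.2.2 points to one conditional probability and the arithmetic to the other, and reference error acts differently on each.

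**Working it through.** **Inputs from the plan.** Reference proportion 0.466, target 0.80, difference 0.334, alpha 5% two-sided, 41 samples, 20% losses, 49 samples (14.2.2); absorbance sensitivity 0.48 (14.2.3.2). **Assumed, because the documents give neither:** absorbance specificity (0.90 to 1.00) and prevalence of haemolysis (5 to 50%).

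**1. The plan's own figure.** One proportion against a reference, with the variance taken at the reference value. The stated power of 1% is read as a 1% type II error, that is, 99% power:

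n = (1.960 + 2.326)² × 0.466 × 0.534 / 0.334² = 40.98, so 41.

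This matches. The 49 follows as 41 × 1.20 = 49.2 (division by 0.80 would give 51.25, so 52). The size is reproduced; what is unclear is the proportion to which it applies.

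**2. What 0.466 is.** (15 − 8)/15 = 7/15 = 0.467. The denominator is the absorbance-positive samples. Writing V for visual and A for absorbance, this is P(V+ | A+), a sensitivity relative to absorbance. A positive predictive value of visual inspection would be P(A+ | V+), with visual positives in the denominator.

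**3. A scale perfect for haemolysis, if the 48% applied here.**

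*True predictive value.* If V equals the truth, P(A+ | V+) = P(A+ | haemolysed) = 0.48, whatever the prevalence or specificity. Reaching 0.80 would need a reference sensitivity of at least 0.80. If all 41 samples were visual positives, the test would reject 0.466 upward (26 or more of 41) with probability about 0.034, and would show 0.80 or more with probability about 0.00002. The plan does not say that the 41 are visual positives, so these two figures are illustrative.

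*The quantity behind 7/15.* With prevalence π and absorbance specificity Sp:

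P(V+ | A+) = 0.48π / [0.48π + (1 − π)(1 − Sp)]

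| Assumed Sp | π = 5% | 10% | 20% | 30% | 50% |
|---|---|---|---|---|---|
| 1.00 | 1.00 | 1.00 | 1.00 | 1.00 | 1.00 |
| 0.95 | 0.34 | 0.52 | 0.71 | 0.80 | 0.91 |
| 0.90 | 0.20 | 0.35 | 0.55 | 0.67 | 0.83 |

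**4. A good but imperfect scale.** Assume visual sensitivity 0.90, visual specificity 0.95, prevalence 30%, and errors independent of those of absorbance. Visual positives make up 0.3 × 0.90 + 0.7 × 0.05 = 0.305 of samples.

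- P(A+ | V+) at Sp 1.00: (0.3 × 0.90 × 0.48)/0.305 = 0.1296/0.305 = 0.425. At Sp 0.90: (0.1296 + 0.7 × 0.05 × 0.10)/0.305 = 0.1331/0.305 = 0.436.
- P(V+ | A+) at Sp 1.00: 0.1296/(0.3 × 0.48) = 0.1296/0.144 = 0.90. At Sp 0.90: 0.1331/(0.144 + 0.7 × 0.10) = 0.1331/0.214 = 0.62.

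The same scale passes or fails 0.80 according to the conditional chosen and the unknown specificity.

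**5. Target taken as the absorbance stage.** Because stages are absorbance ranges, a scale perfect for that target scores 1.00 on every measure. So does one that copies absorbance exactly; if the 48% held, that scale would still detect only 48% of haemolysed samples. Agreement can be estimated from these data. Accuracy for haemolysis cannot, without outside assumptions.

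**The case against.** A reader might infer that even a perfect visual scale must score 0.48 and fail the 0.80 target. The documents do not support that. The 0.466 conditions on absorbance-positive samples, and for that quantity a perfect scale can score up to 1.00. Nor can the 48% be carried over as fixed: its cut-off and comparator are not stated, this plan uses several stage cut-points taken from another scale, and 14.2.3.2 itself warns about extrapolation.

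A reader might also infer that 9.7.3 and 14.2.3.2 flatly contradict each other. Being sensitive to changes can mean that a continuous reading responds to small differences, which is compatible with low diagnostic sensitivity at a threshold. The 48% is disclosed openly, with reasons for keeping the method, including "The rest of the precision values of this diagnostic technique are within the ranges considered acceptable (52").

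The plan also deals with other measurement problems: bilirubin and lipaemia interference, three repeated absorbance readings, and observer agreement. Criterion validity is already introduced as concordance with absorbance, so part of the remedy is there in substance.

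All of this stands, and it removes any firm prediction that a correct scale would be rejected. It does not supply a method for reference error, a definition of positive prediction, or a basis for an H1 about haemolysis when absorbance is the only criterion. Repeated readings address precision, not systematic misses.

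**Conclusion.** The point holds as a limit on what may be concluded. With absorbance as the only standard and stages defined from it, the analysis can establish agreement with absorbance. Calling the results sensitivity, specificity and predictive values, and concluding that haemolysis intensity is optimally predicted, goes beyond the data.

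The numerical effect is conditional. The value of 0.48 for a perfect scale requires both that positive prediction is P(A+ | V+) and that the 48% applies to this device, plasma and set of cut-points. Under P(V+ | A+), and still taking the 48% as given, the value is 1.00 with perfect specificity and about 0.20 to 0.91 over the assumed ranges. The mislabelling of 7/15 needs none of these assumptions; it follows from the counts in 14.2.2.

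This concerns the main secondary variable. The primary venipuncture endpoint is not affected. It is an inexpensive improvement, not a flaw that invalidates the trial.

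**What to change.** 1. In 14.2.2, define the tested quantity as positive percent agreement with the absorbance stage, P(V+ | A+), which is what 7/15 measures, and drop the predictive-value label. State that its denominator is the absorbance-positive samples, so that it is clear which samples the 41 refers to.
2. In 14.2.3.3.2, report positive and negative percent agreement of the observers with the absorbance stage.
3. Limit H1 and its conclusion to agreement with absorbance.
4. If accuracy for haemolysis is still reported, add a sensitivity analysis over reference sensitivity from 0.48 to 1.0 and a stated range of reference specificity, once with independent errors and once with errors shared by observer and absorbance.
5. In 9.7.3, clarify that sensitivity to changes does not mean diagnostic sensitivity, and refer to the 48% in 14.2.3.2.

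The cost is SAP wording and a few lines of analysis on data already planned. The price is a narrower claim: the scale would be reported as agreeing with absorbance, not as validly detecting haemolysis.

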9.8. RISKS-BENEFITS

A. RISKS

Derived from interventions

Possible local erythema due to the application of dry topical heat. They have only been registered in those individuals that denote "sensitive" skins; without being visible in "non-sensitive" skins. In addition, it has been documented that it remits after a few minutes without the need for treatment (37).

Possible transient paresthesia in the arm applied the high pressure with the sphygmomanometer because of overcoming an average blood pressure of 100 mmHg. No case has been documented

(37) although the possibility of it is considered. It is solved assuring the presence of radial pulse in mentioned upper limb.

Derived from venipuncture

Possible hematoma and pain due to the venipuncture procedure itself. As well as a vasovagal syncope. The sensation of pain due to the pressure exerted by the elastic compressor is also contemplated, whose origin is attributed to the type of material rather than the pressure exerted.

Derived from the evaluation of blood samples

No risk has been registered, neither direct nor indirect, for the observation of plasma in blood samples.

B. BENEFITS

Beneficial effects have been registered in the increase of the antebrachial venous perception, previous step to the venipuncture, with the combined application of pressure and heat (37). Therefore, it suggests a possible beneficial effect in successful intravenous cannulation in a smaller number of attempts.

No direct benefit has been recorded on the patient in observing the plasma of the blood samples. However, it could be considered that the indirect benefit would be directly related to the transcendence of the clinical findings.

A. EVALUATION OF THE RISK-BENEFIT BALANCE

As a consequence, the local erythema that remits in minutes would reflect greater benefit than the appearance of hematoma of prolonged duration to days; produced by failed intravenous lines. The transient paresthesia, with easy solution, could reduce the pain perceived by the subject, whose impact would be beneficial. Both the pain of venipuncture and vasovagal syncope occur with reduction thereof, the lower the number of attempts at venipuncture.

It implies an increase in resources for a second or third intravenous cannulation, both of material resources involved in the technique of venipuncture as well as that for the treatment of hematoma and vasovagal syncope, as well as the time of the nurses. To this is added the opportunity time; the lack of investment in other objectives or activities, and the discomfort of the subject.

The transcendence of the clinical findings of hemolysis would exceed the possible discomfort generated by the observation of one-two microliters of plasma.

As a result of what has been described above, it could be concluded that the attributed benefits outweigh the acceptable risks.

9.9. FINISHING OF FIELD WORK

It is considered that the fieldwork has ended when the randomly assigned arm and venipuncture have been applied on the first attempt to the subject number 54. In the case in which any of the subjects had adverse reactions, the completion of the fieldwork of the patient will be prolonged until the reaction ceases. At that moment the data entry begins in the SPSS v23 program.

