2.13. Subjects and sample size

Population. Adult healthy subjects.

Sample size. It is required to enroll 54 subjects with a 95% of level of confidence and 80% level of power.

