5. CA + P -> C. Combination of dry topical heat and high stagnation pressure in the first period. Comparator in the second period.

6. C-> PA + C. Comparator in the first period. Combination of dry topical heat and high stagnation pressure in the second period.

As a result of these options and the coverage of the Clinical Trials Unit of the University Hospital of La Princesa is twelve individuals in each group, the following sealed envelopes for each group are established

- Four contain topical heat and comparator intervention

- Two will be topical first period heat. Comparator in the second -> [CA-> C]
- Two will be comparator in the first period. Topical heat in the second -> [C-> CA]

- Four intervention of high pressure and comparator

- Two will be high pressure in the first period. Comparator in the second -> [P-> C]
- Two will be comparator in the first period. High pressure in the second -> [C-> P]

- Four combined (topical heat and high pressure) and the comparator

- Two will be combination in the first period. Comparator in the second -> [CA + P-> C]
- Two will be comparator in the first period. Combination in the second -> [C-> CA + P]

This scheme of twelve envelopes will be carried out five times to address a sufficient sample size, of sixty subjects, to assume the estimated losses and, finally, to obtain the number of subjects, who have completed both periods, calculated to obtain a statistical significance of the results.

Due to the inclusion / exclusion criteria established, and which will result from the first evaluation VIA (36), an equivalent number of individuals in each arm will be sought.

In each envelope, the chronological order of application of the intervention-comparator will be included, by default and without previous knowledge.

It will be randomized only once, in the first period. In the second period, the remaining sequence will be applied. Figure 1

[figure not shown]

Figure 1. Design flow diagram. Own elaboration.

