14. STATISTICAL ANALYSIS PLAN

14.1. Main analysis

14.1. 1. Definition of variables

Primary variable

Successful venipuncture at the first attempt. Dichotomous qualitative variable. Success / Failure

Secondary variables

Successful venipuncture frequency. Discrete quantitative variable. (1,2,3,4)

Visual intensity of hemolysis. Discrete quantitative variable. It is measured in stadiums.

Scale of expressed pain intensity (VAS). Discrete quantitative variable.

Scale skin types Fitzpatrick. Discrete quantitative variable.

Ingestion of liquids (less than 500 ml) in the last 6-8h prior to cannulation. Discrete quantitative variable (measured in glasses); it will be transcribed continuously for statistical analysis.

Affiliation of individuals

Respected fasting of 6-8 hours. Dichotomous qualitative variable.

Age. Quantitative variable continues.

Sex. Dichotomous qualitative variable.

Race. Discrete quantitative variable. 1 -> Caucasian 2 -> Black 3 -> Asian 4 -> Latin

BP. Continuous quantitative variable.

HR. Continuous quantitative variable.

T. Continuous quantitative variable.

BMI Continuous quantitative variable.

14.1. 2. Sample size calculation

The sample calculation is performed with the GRANMO calculator (63). It assumes a random risk (alpha) of 5% and a statistical power (beta) of 80%; for which it is tried to prove the veracity of the null hypothesis, of bilateral type.

That is, the risk of rejecting the null hypothesis when this is true is 5%, and the probability of not rejecting it being false is 20%.

In the literature, the success of peripheral intravenous canals was recorded in the first attempt, using the usual technique, in 74% of the cases (55). Currently, a proportion of peripheral intravenous cannulation has been registered at the first attempt of 73%, in an ultrasound ecoguided manner (33). In relation to the second successful attempt, in the usual clinical practice it amounts to 92% of the cases and, in the ultrasound ecoguided to 91% (33.55).

For the present work we intend to achieve a 95% success rate in antebrachial venous cannulation at the first attempt. Thus, overcome with one of the alternative methods proposed in this study the cumulative proportion of the second attempt of the usual and eco guided clinical practice.

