It is considered a clinically relevant difference the successful venous cannulation at the first attempt when, not only allows the cannulation at the first attempt of those cases that hypothetically would be observed, but accumulate to those cases that, in a way observed in the literature, the cannulation has been achieved at the second attempt, and hypothetically, that success can be achieved in the first attempt.

The comparative indicators are based on the comparison method and the reduction of intraindividual variability. It is considered a root of the experience, one of them is lost; An average of both percentages has been made, thus obtaining a 12% loss approximately.

Therefore, the calculation of the sample size should be followed through the modality of proportions, paired measures (repeated in a group). Fix in the proportion with pre-intervention event 0.74, in the proportion with post-intervention event 0.95, and the loss ratio 0.12.

Finally, the estimated sample size is 60 subjects.

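### The abstract and the end-of-fieldwork rule use 54 subjects, the SAP and the envelopes use 60, and no section says whether 54 counts enrolled subjects or completers of both periods

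*Combined protocol and SAP*

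**What the plan says.** Four places in the combined protocol and SAP set the size of the trial.

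- **Section 2.13 (abstract):** "It is required to enroll 54 subjects with a 95% of level of confidence and 80% level of power".
- **Section 9.9:** fieldwork is over once the assigned arm and "venipuncture have been applied on the first attempt to the subject number 54". Data entry then begins, unless an adverse reaction is still being followed. The section does not say whether that subject is the 54th enrolled or the 54th to complete, and it does not mention period 2.
- **Section 6.3:** "This scheme of twelve envelopes will be carried out five times to address a sufficient sample size, of sixty subjects". The stated purpose is to absorb the expected losses and still reach the calculated number of subjects with both periods completed. That number is not given there.
- **Section 14.1.2:** the inputs to the paired-proportions calculation are "Fix in the proportion with pre-intervention event 0.74, in the proportion with post-intervention event 0.95, and the loss ratio 0.12", with two-sided alpha of 5% and power of 80%. The result is: "Finally, the estimated sample size is 60 subjects".

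Two other sections matter. Section 7.4 counts a subject who misses the second period as lost and analyses per protocol. Section 14.1.3.1.1 names McNemar's test as the primary test, without saying whether it is exact, continuity-corrected or uncorrected.

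**The concern.** The primary test uses within-subject pairs, so the rule that ends fieldwork decides how many pairs there are. That rule carries the smaller figure. The abstract attaches the same figure to the verb enrol and to 80% power, yet the SAP's enrolment figure for 80% power is 60.

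A team following sections 2.13 and 9.9 literally could close the trial six subjects short of the calculated size. It could also close before the last subjects have had their second period. A team following sections 6.3 and 14.1.2 would open all 60 envelopes. The two teams would analyse different numbers of pairs under the same protocol.

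**Working it through.** **Inputs.** From section 14.1.2: success 0.74 and 0.95, so d = 0.21; two-sided alpha 0.05 (z = 1.960); power 80% (z = 0.842); loss 0.12. From section 6.3: five blocks of 12, each with two envelopes for each of six sequences.

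**Assumption.** The proportion of discordant pairs, ψ, is not stated. I use two values:

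- Independent responses within a subject: 0.26 × 0.95 + 0.74 × 0.05 = 0.247 + 0.037 = 0.284.
- The maximum that the two rates allow: 0.26 + 0.05 = 0.31.

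**Step 1: reproduce the plan's 60.** The normal approximation for McNemar's test is n = [1.960·√ψ + 0.842·√(ψ − d²)]² / d², with d² = 0.0441.

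- ψ = 0.31: (1.091 + 0.434)² / 0.0441 = 52.75 pairs, and 52.75 / 0.88 = 59.9, so 60. (Rounding up to 53 before inflating gives 60.2, so 61.)
- ψ = 0.284: (1.045 + 0.412)² / 0.0441 = 48.1 pairs, and 48.1 / 0.88 = 54.7.

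So 60 is a figure with losses already included, and about 53 complete pairs lie behind it.

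**Step 2: place 54 against 60 and 12% loss.**

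- 60 × 0.88 = 52.8 expected completers from 60 randomised.
- 54 × 0.88 = 47.5 expected completers from 54 enrolled.
- 54 / 0.88 = 61.4 to be randomised for 54 expected completers.
- 54 × 1.12 = 60.5, if the loss is added rather than divided out.

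Read as completers, 54 lies within one or two subjects of the plan's figures. Read as enrolled, it is six below 60.

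**Step 3: power under each reading.** The approximation is Φ{[d√n − 1.960√ψ] / √(ψ − d²)}. For 47 pairs and ψ = 0.31 this is Φ{(1.440 − 1.091) / 0.516} = 75.0%. The other three columns sum exactly over the number and split of discordant pairs.

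| Pairs | ψ | Normal approx. | Exact McNemar | Continuity-corrected | Uncorrected |
|---|---|---|---|---|---|
| 47–48 (54 enrolled) | 0.31 | 75.0–76.0% | 70.1–71.3% | 68.6–69.7% | 77.8–78.8% |
| 47–48 (54 enrolled) | 0.284 | 79.0–79.9% | 75.2–76.4% | 74.5–75.6% | 82.4–83.3% |
| 53 (60 randomised) | 0.31 | 80.2% | 76.8% | 74.9% | 83.3% |
| 53 (60 randomised) | 0.284 | 83.9% | 81.6% | 80.5% | 87.3% |
| 54 completers | 0.31 | 81.0% | 77.8% | 75.9% | 84.1% |
| 54 completers | 0.284 | 84.6% | 82.5% | 81.3% | 88.0% |

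These figures pool all three interventions against the comparator, as the plan's 60 does.

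**Step 4: does each reading work as an end rule?**

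- *Enrolled.* 54 / 12 = 4.5 blocks. After four blocks each arm has 16 subjects. The next six envelopes could split the arms as unevenly as 20/18/16, and equal sequences are no longer guaranteed.
- *Completers.* If each of 60 subjects completes independently with probability 0.88 (my assumption), the chance of 54 or more completers is about 41%. More often than not the end point would not be reached, and section 9.9 does not say what happens then.

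**The case against.** The best defence is that section 6.3 already reconciles the numbers: 60 are randomised to absorb losses, and a smaller number completes both periods. The loss rate is itself called approximate, and 52.8 is close to 54. On that reading 54 pairs slightly exceed the roughly 53 behind the plan's 60. This stands. A reader might infer that no reading reconciles 54, 60 and 12% loss; the documents do not support that.

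A reader might also infer that stopping at 54 misses 80% power outright. That does not follow either. It depends on 54 meaning enrolled, and then on choices the SAP leaves open. The uncorrected test under independence still gives 82–83% at 47 to 48 pairs. Positive within-subject correlation, which a subject-as-own-control design anticipates, lowers ψ and raises power: at the minimum ψ of 0.21 it is about 95% even with the exact or corrected test. At ψ = 0.31 the corrected test gives only 74.9% at the plan's own 53 pairs, so part of any shortfall comes from the test and discordance chosen, not from 54 against 60.

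The balance point is also modest. Subjects are handled in groups of twelve, losses would disturb balance anyway, and the pooled test does not need equal arms.

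The defence still has to be inferred. No section defines 54 as completers, section 2.13 says enrol, and section 9.9 omits period 2. Even when granted, it leaves an end point that may never be reached.

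**Conclusion.** The text conflicts and has to be corrected before recruitment, because it governs the number of pairs in the primary analysis. Sections 6.3 and 14.1.2 agree on 60, and that figure reproduces from its inputs. Sections 2.13 and 9.9 do not match it as worded.

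The size depends on what 54 means. As enrolled, it leaves 47 to 48 pairs and power of about 75–80% by the approximation that reproduces 60 (69–76% with exact or continuity-corrected McNemar, 78–83% uncorrected), and enrolment stops within the fifth block. As completers, power is about 81–85% by the same approximation, but 60 randomised give 52.8 expected completers, so the rule may never be met. All these figures assume success rates of 0.74 and 0.95, 12% loss and ψ between 0.284 and 0.31. A loss of power is therefore a conditional consequence; the contradiction and the incomplete end rule are not conditional.

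**What to change.** - **Section 2.13:** state that 60 subjects are randomised in five complete blocks of 12, and that about 53 are expected to complete both periods.
- **Section 9.9:** end fieldwork when all five blocks have been allocated and the last subject has completed period 2 or been lost. Keep the existing extension for unresolved adverse reactions. The end of fieldwork then no longer depends on a completer count that may not occur.
- **If the sponsor does intend to stop at 54 enrolled:** say so in sections 6.3 and 14.1.2 as well, and restate the power for 47 to 48 pairs together with the form of McNemar's test and the discordance assumed.

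The cost is a change of wording in two places. It requires no subjects beyond the 60 already planned.
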